14.3 Statistical analysis

14.3.1 Disposition of subjects

The reasons for permanent discontinuation of IMP and withdrawal from trial will be presented for all randomised subjects by treatment group.

14.3.2 Demographics and other baseline characteristics

Descriptive statistics of demographics and other baseline characteristics will be presented for all randomised subjects by treatment group. Presentations of demographics, baseline disease severity, and proportion of subjects with baseline worst pruritus (weekly average) above/below 4 on the numeric rating scale (NRS), i.e., one of the symptoms captured in the HESD, will also be given by region and baseline disease severity.

Demographics include age, sex, ethnicity, and race. Other baseline characteristics include vital signs, height, weight, body mass index, total IgE, Fitzpatrick skin type, duration and classification of chronic hand eczema, concurrent diagnoses (from medical history and indications for concomitant medication), concomitant medication, and previous chronic hand eczema treatments.

14.3.3 Exposure and treatment compliance

The duration of exposure to treatment in a specific visit interval will be calculated as the number of days from date of first application of IMP in that period to the date of last application of IMP in that period, both days included.

Exposure to treatment will be presented for the safety analysis set as days of exposure per treatment group.

Drug accountability data will be calculated by subtracting the weight of the used tubes from the mean normal weight of full tubes. Average weekly/bi-weekly and total usage will be presented per treatment group, respectively, both for time intervals between visits (1 or 2-week periods depending on the time between site visits) and total period.

Adherence to treatment regimen will be recorded in the eCRF. If any complications or deviations in administration are observed, these will be described as protocol deviations.

Adherence will be presented for the safety analysis set for each treatment group via the percentage of applications missed.

14.3.4 Testing strategy

This is a dose-ranging trial with the primary objective to establish the dose-response relationship. For the primary endpoint IGA TS and the secondary endpoint change in HECSI from baseline to Week 16, the selection of the dose-response model that fits data best will be controlled using a family-wise error rate of 5%. There will be no adjustment for the multiple testing of primary and secondary endpoints, all p-values will be considered nominal.

14.3.5 Analysis of primary efficacy endpoint

The primary endpoint IGA TS at Week 16 will be analysed for the full analysis set and for the per protocol analysis set. The per protocol analysis is regarded as supportive.

IGA TS refers to IGA score of 0 (clear) or 1 (almost clear) with ≥ 2 -step improvement from baseline.

For the analysis of the primary endpoint, subjects who initiate rescue medication before Week 16 or withdraw from the trial and have no retrieved data at Week 16, will all be considered non-responders.

The Multiple Comparison Procedure – Modelling (MCP-Mod) approach (see e.g., EMA Qualification Opinion of MCP-Mod [23] or Bretz et al [24] for further details of the framework) will be used to guide dose selection. The dose-response relationship for the binary endpoint IGA TS will be modelled by the following 3 identified candidate models. These candidate models are selected based on the expected dose-response.

Linear in log: $E_0 + \delta \times \log(d + c)$,

E_{max} : $E_0 + E_{max} \times d / (ED_{50} + d)$,

Sigmoid E_{max} : $E_0 + E_{max} \times d^h / (ED_{50}^h + d^h)$,

where d is the dose (incl. vehicle), E_0 is the efficacy offset (anticipated vehicle effect), E_{max} is the asymptotic maximum effect, ED_{50} is the half-life value of E_{max} , h is the steepness at ED_{50} , δ is the slope parameter, and c is a fixed offset parameter.

The models will be adjusted for the stratification variables region and baseline IGA. The model parameters (ED_{50} , h) will be prespecified a priori by suitable guesses based on data from Japan Tobacco's dose-ranging trial QBA2-1 (25). Akaike's Information Criteria will be

used as the goodness-of-fit criterion that will drive the selection of the dose-response model that fits data best while controlling the family-wise error rate at 5%. Based on the selected model, the dose-response relationship will be estimated and presented with 2-sided 95% CI. If none of the candidate models converge, other possibilities of models and goodness-of-fit criteria will be explored. The dose-response modelling will be performed on both the total population and subjects having a baseline IGA of 3 or 4, in order to further explore heterogeneity in the disease population.

In addition to the dose-response modelling approach, the difference in response rates between the delgocitinib doses and vehicle will be analysed separately for each of the dose groups using the Cochran-Mantel-Haenszel test stratified by region (Europe and North America) and disease severity (baseline IGA of 2, 3, and 4). The null hypothesis of no difference in response rates between delgocitinib and vehicle will be tested against the 2-sided alternative that there is a difference.

Sensitivity analysis will be performed as applicable in order to assess the robustness of results of the primary analysis with respect to the retrieved data at Week 16, use of rescue medication, and assumptions regarding missing data. This will be described in further detail in the statistical analysis plan.

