Primary objective	
Primary and secondary endpoints
 
Primary endpoint
 
 Investigator's Global Assessment (IGA) score of 0 (clear) or 1 (almost clear) with at least a 2-step improvement (IGA TS) from baseline to Week 16. 
Secondary endpoints
 
 Change in Hand Eczema Severity Index (HECSI) from baseline to Week 16. Time to IGA TS.
Other objectives	
Other endpoints
 
Safety and tolerability
 
 Number of adverse events (AEs). 
Health-related quality of life and efficacy
 
 Change in Chronic Hand Eczema Symptom Diary (HESD) (weekly average for each individual symptom) from baseline to Week 16. 
 Reduction in worst pruritus ("itch" – one of the symptoms captured in HESD) (weekly average) of ≥ 4 points from baseline to Week 16 among subjects with baseline worst pruritus (weekly average) ≥ 4. Change in Chronic Hand Eczema Impact Scale (HEIS) from baseline to Week 16. Patient's Global Assessment (PaGA) TS at Week 16. PaGA TS refers to achieving: PaGA score of 0 (clear) when classified at baseline as 1 (almost clear) or 2 (mild), or PaGA score of 0 (clear) or 1 (almost clear) when classified at baseline as 3 (moderate) or 4 (severe). Time to PaGA TS.

Objectives	Endpoints

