Patients with hand eczema represent a heterogeneous patient population as hand eczema is associated with different aetiologies and morphologies and the severity may range from mild to severe. To mitigate any potential difference in trial outcome based on baseline characteristics, the trial subjects will be randomised in stratified manner as described in Section 9.3. The randomisation will minimise selection bias and minimise influence of (intrinsic) confounding factors and the stratification will ensure a certain balance of the treatment groups with respect to disease severity and region. The enrolment is controlled by disease severity to allow for assessment of co-variability in patients with mild, moderate, and severe disease state.

The inclusion of 4 active treatment groups with 1, 3, 8, and 20 mg/g of delgocitinib cream and a vehicle control group is considered enough to establish a dose-response signal. The vehicle control group will serve as reference and has been added to establish the efficacy and safety of delgocitinib cream in a blinded trial design.

The trial endpoints have been selected to evaluate the efficacy of delgocitinib in improving the severity and extent of chronic hand eczema. Both IGA and HECSI will be used in this clinical trial as investigator-rated assessments of disease severity. The IGA is an assessment of the overall disease severity at a given time point and is based on a 5-point scale describing the severity of the disease from “clear” to “severe”. The HECSI is an instrument used to score both the extent and the intensity of the disease. The primary endpoint of the trial is to evaluate the percentage of subjects achieving treatment success defined as an IGA score of 0 (clear) or 1 (almost clear) with at least a 2-step improvement from baseline to Week 16. The trial endpoints will also address subject’s perception of disease severity and the impact on sleep, daily activity, and health-related quality of life.

13 Adverse events

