14.3.6 Analysis of secondary efficacy endpoints

The secondary endpoints change from baseline to Week 16 in HECSI and time to IGA TS will be analysed for the full analysis set and for the per protocol analysis set. The per protocol analysis is regarded as supportive.

For the analysis of the change from baseline to Week 16 in HECSI, data collected after permanent discontinuation of IMP or after initiation of rescue medication will not be included in the analysis. Missing data at Week 16 will be imputed using the mixed model for repeated measurements (MMRM) predicted values from the below specified model for repeated measurements.

The dose-response modelling approach suggested for the primary endpoint will also be applied for the continuous endpoint change from baseline to Week 16 in HECSI.

In addition to the dose-response modelling approach, the continuous endpoint will be analysed using a MMRM on the post baseline responses up to Week 16 with an unstructured

covariance matrix, Kenward-Roger approximation to estimate denominator degrees of freedom, and the mean modelled as follows:

Change from baseline in HECSI

$$= \text{treatment} \times \text{visit} + \text{baseline HECSI} \times \text{visit} + \text{region} + \text{baseline IGA}$$

The estimates will be presented with nominal p-values and 95% CI at each visit. The primary comparison between each delgocitinib dose and vehicle will be at Week 16.

Time to IGA TS response is defined as the time from baseline to first assessment of an IGA TS. Subjects will be censored at the date of the last assessment visit or at initiation of rescue medication, whichever occurs first. Kaplan-Meier curves of time to IGA TS will be estimated and presented by treatment for the full analysis set. Treatment groups will be compared using a 2-sided log-rank test stratified by region and baseline IGA.

Sensitivity analysis will be performed as applicable in order to assess the robustness of results of the primary analysis with respect to the retrieved data at Week 16 and assumptions regarding missing data. This will be described in further detail in the statistical analysis plan.

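### The HECSI dose-response model leaves out baseline HECSI, so the curve is estimated less precisely than the data allow

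*Combined protocol and SAP*

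**What the plan says.** Section 14.3.5 sets out the MCP-Mod analysis of IGA treatment success, with linear-in-log, Emax and sigmoid Emax candidates, and fixes the covariates: "The models will be adjusted for the stratification variables region and baseline IGA".

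Section 14.3.6 then says: "The dose-response modelling approach suggested for the primary endpoint will also be applied for the continuous endpoint change from baseline to Week 16 in HECSI". No covariate is added there.

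The next paragraph of Section 14.3.6 specifies a second analysis: "In addition to the dose-response modelling approach, the continuous endpoint will be analysed using a MMRM". Its mean model contains treatment by visit, baseline HECSI by visit, region and baseline IGA.

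On incomplete data the section says: "Missing data at Week 16 will be imputed using the mixed model for repeated measurements (MMRM) predicted values". The predictions come from that same MMRM. Nothing says that the dose-response curve is fitted to the MMRM estimates.

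**The concern.** One endpoint has two models with different covariates, and no reason is given. The model without the baseline value is the one that serves the trial's primary objective, the dose-response relationship (Section 14.3.4).

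Baseline IGA is a weak stand-in for baseline HECSI. It has three levels at entry (Section 7.2), and Panel 9 grades the intensity of signs with no term for area. Section 12 says of the other scale: "The HECSI is an instrument used to score both the extent and the intensity of the disease". Section 11.3.2 multiplies severity by area in five hand regions, up to 360. Subjects in one IGA class can therefore start from very different HECSI scores, and their scope for change differs accordingly.

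At stake are the power of the HECSI contrast test, the reliability of the AIC-based choice of model, and the width of the confidence intervals around the curve. Baseline HECSI imbalance that arises by chance within IGA strata, between arms of 50, also stays in the dose estimates uncorrected.

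**Working it through.** **The plan's own figure.** Section 14.1 gives power for IGA treatment success only: 45% against 15%, 50 per arm, two-sided 5%. The pooled normal approximation gives (0.30 − 1.96 × √(2 × 0.30 × 0.70/50)) / √((0.45 × 0.55 + 0.15 × 0.85)/50) = (0.30 − 0.180)/0.0866 = 1.39, a power of 91.8%. This agrees with the plan's statement of slightly above 90%. It is not affected by this point. No power, SD or correlation is given for HECSI, so what follows rests on assumptions.

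**Spread within one IGA class.** Mild erythema with moderate vesicles fits IGA 3 in Panel 9. By Panels 11 and 12:

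- fingertips only, area score 1: (1 + 2) × 1 = 3;
- all five regions, area score 4: 5 × (1 + 2) × 4 = 60.

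The same signs in the same IGA class can thus differ 20-fold in HECSI.

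**Precision, first form.** Let r be the overall correlation of baseline and Week 16 HECSI, with equal variances scaled to 1, and let R² be the share of baseline HECSI variance explained by baseline IGA. Assume also that IGA predicts Week 16 HECSI only through baseline HECSI.

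- Residual variance of change given IGA: (1 − r)²(1 − R²) + (1 − r²).
- Residual variance with baseline HECSI added: 1 − r².
- Ratio: (1 + r) / [(1 − r)(1 − R²) + (1 + r)].

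| r | R² | Ratio | Equivalent extra subjects |
|---|---|---|---|
| 0.3 | 0.2 | 1.3/1.86 = 0.70 | 43% |
| 0.3 | 0.4 | 1.3/1.72 = 0.76 | 32% |
| 0.5 | 0.4 | 1.5/1.80 = 0.83 | 20% |
| 0.5 | 0.6 | 1.5/1.70 = 0.88 | 13% |
| 0.7 | 0.6 | 1.7/1.82 = 0.93 | 7% |

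**Precision, second form.** Work within IGA and region strata, so that the third assumption is not needed. Let r be the within-stratum correlation and k the ratio of the Week 16 SD to the baseline SD. The ratio is k²(1 − r²)/(1 + k² − 2rk), which equals one minus the squared correlation of change with baseline.

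| k | r = 0.1 | r = 0.3 | r = 0.5 | r = 0.7 |
|---|---|---|---|---|
| 1 | 0.55 | 0.65 | 0.75 | 0.85 |
| 0.75 | 0.39 | 0.46 | 0.52 | 0.56 |
| 0.5 | 0.22 | 0.24 | 0.25 | 0.23 |

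At k = 1 the standard error falls by 8% (r = 0.7) to 26% (r = 0.1), and 50 per arm acts like 59 to 91. A contrast with 80% power unadjusted would have 86% to 96.5%. Simulating an Emax contrast with five arms of 50, with region and IGA in both models, gave ratios within about 0.01 of these (0.754 against 0.750 at r = 0.5, k = 1).

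**Why the two ranges differ.** The first form implies k above 1 within strata. At r = 0.5 and R² = 0.4, the within-stratum variances are 0.60 at baseline and 0.25 × 0.60 + 0.75 = 0.90 at Week 16. So k² = 1.5, and the within-stratum r is 0.5 × √(0.60/0.90) = 0.41. The second formula then gives 1.25/1.50 = 0.83, the same answer. The first range is the more cautious.

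**When the loss is zero.** Only when r × k = 1, that is, when change is uncorrelated with baseline within strata. If the Week 16 SD is no larger than the baseline SD, this requires r = k = 1.

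**Chance imbalance.** Between two arms of 50, the difference in mean baseline HECSI within strata has an SD of √(2/50) = 0.20 baseline SDs. The slope of change on baseline is rk − 1, or −0.5 at r = 0.5 and k = 1. A one-SD imbalance therefore moves the unadjusted difference by 0.20 × 0.5 = 0.10 baseline SDs.

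**The case against.** The strongest reply is that the omission is inferred. The covariate sentence is written for IGA treatment success, and Section 14.3.6 imports an approach without saying that its covariate list is complete. Section 14.3.12 leaves the SAP to be finalised before unblinding, and no separate SAP text on this model is in the documents. That is fair as far as it goes. But the imported approach states its covariates, nothing adds to them, and the MMRM beside it lists baseline HECSI explicitly. Read as written, the dose-response model lacks it.

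Second, the MMRM already uses baseline HECSI for every dose-against-vehicle estimate, and it supplies the imputed values. This stands as a limit on scope: the loss is confined to the HECSI curve, its contrast test and its model selection. It does not repair those, because the curve is not said to be fitted to MMRM output.

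Third, in a randomised trial, omitting a prognostic covariate from a linear model causes neither bias nor an inflated type I error. HECSI is also a secondary endpoint with nominal p-values. Stratification by IGA and use of a change score already remove part of the imbalance. All true, and reasons to treat this as a recommended improvement rather than a flaw in validity.

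Fourth, the size is not established by the documents, and the cautious form needs an assumption about how IGA acts. At its low end the standard error falls by only about 3% (1 − √0.934). The figures are illustrative, but both forms show a loss throughout the ranges examined.

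**Conclusion.** The point holds. As written, the HECSI dose-response model adjusts for region and baseline IGA but not for the baseline of its own change score, and so is less precise than it could be. Under the cautious assumptions (equal overall variances, correlation 0.3 to 0.7, IGA explaining 20% to 60% of baseline HECSI and acting only through it), adding baseline HECSI cuts residual variance by 7% to 30%, equivalent to 7% to 43% more subjects. If the Week 16 SD is no larger than the baseline SD within strata, the gain is larger: a ratio of 0.85 or below over the values examined. The planned analysis remains valid, and neither IGA treatment success nor the pairwise MMRM is affected.

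**What to change.** State in Section 14.3.6 and in the SAP that the dose-response model for change in HECSI is adjusted for baseline HECSI as well as region and baseline IGA, in line with the MMRM. Apply this to the contrast test, the model fits and the confidence intervals, and also in the subset with baseline IGA 3 or 4 if HECSI is modelled there. An alternative is to fit the curve to the Week 16 dose estimates from the MMRM and their covariance matrix, which makes the two analyses agree by construction.

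The cost is one phrase, settled before the randomisation code is broken. Baseline HECSI is already scheduled at screening and Day 1 (Panel 2) and already in the MMRM. With all 250 subjects the covariate uses one residual degree of freedom out of 250 − 5 arms − 1 for region − 2 for IGA = 242.

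### The 95% CI of the primary dose-response curve ignores the AIC model selection and under-covers at 1, 3 or 8 mg/g if the true curve is a steep sigmoid

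*Combined protocol and SAP*

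**What the plan says.** Section 14.3.5 uses MCP-Mod for IGA treatment success at Week 16 with three candidates: linear in log dose, Emax and sigmoid Emax. AIC is "used as the goodness-of-fit criterion that will drive the selection of the dose-response model that fits data best". The presented result follows from that single choice: "Based on the selected model, the dose-response relationship will be estimated and presented with 2-sided 95% CI".

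On the shape parameters, ED50 and h "will be prespecified a priori by suitable guesses"; no values are given. The list of symbols ends "and c is a fixed offset parameter", again without a value. There is a fallback: "If none of the candidate models converge, other possibilities of models and goodness-of-fit criteria will be explored". The modelling is also repeated in a subset: "The dose-response modelling will be performed on both the total population and subjects having a baseline IGA of 3 or 4". Section 14.3.6 carries the approach over to change in HECSI.

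Two passages might have dealt with the selection but do not. Section 14.3.4 says "the selection of the dose-response model that fits data best will be controlled using a family-wise error rate of 5" per cent, which concerns testing and choosing a model, not interval coverage. The sensitivity analyses of the primary endpoint are planned "with respect to the retrieved data at Week 16, use of rescue medication, and assumptions regarding missing data"; model choice is not among them. Section 14.3.12 leaves the SAP to be finalised before unblinding, so the point can still be settled there.

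**The concern.** A CI computed as if the selected model had been fixed in advance leaves out the uncertainty about which model is right. AIC also favours simpler curves when data are sparse. With five dose groups of 50 it will often prefer a log-linear or Emax curve to a true sigmoid, and the resulting band is then both too narrow and in the wrong place.

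The curve and its band are the presented answer to the primary objective and are meant to guide dose selection for phase 3. If the band sits above the truth at a low strength, a nearly inactive strength looks better than it is, under a stated 95%. Sigmoid Emax is one of the three shapes that the plan itself regards as expected, so this case is not remote from the design.

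**Working it through.** **1. The plan's own figure.** Section 14.1 gives 45% versus 15%, 50 per group, 5% level. Pooled normal approximation: SE under the null = √(2 × 0.30 × 0.70 / 50) = 0.0917; SE under the alternative = √((0.15 × 0.85 + 0.45 × 0.55) / 50) = 0.0866. Power = Φ((0.30 − 1.96 × 0.0917) / 0.0866) = Φ(1.39) = 91.8%. The statement of slightly above 90% reproduces. It concerns one pairwise comparison and says nothing about the curve's CI.

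**2. Two readings of section 14.3.5.**
- Reading A: ED50 and h are guessed for the contrast test but estimated in the modelling step. Only c is called fixed, and a provision for non-convergence would hardly be needed if ED50, h and c were all fixed.
- Reading B: ED50 and h are held at the guesses.

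**3. Assumed truths.** On the logit scale, logit p(d) = −1.735 + 1.534 × f(d)/f(20), where −1.735 = logit 0.15, 1.534 = logit 0.45 − logit 0.15, and f(d) = d^h / (ED50^h + d^h). Assumed, because the plan gives none: ED50 2, 3, 4, 6; h 1.5, 2, 3; c 0.2 and 1. Flat, log-linear and Emax truths were also run.

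**4. Why a simpler curve wins, by example.** Take ED50 3, h 3. At 1 mg/g, f(1)/f(20) = 0.0357/0.9966 = 0.0358, so the logit is −1.680 and the true response 15.7%. A log-linear curve (c = 0.2) through the true end points gives log(6)/log(101) = 0.388, logit −1.139, response 24%. The gap is 0.54 logits against an arm SE of 1/√(50 × 0.157 × 0.843) = 0.39, about 1.4 SE. At 8 mg/g the same curve gives 38% against a true 43%, under 1 SE. The AIC penalties are 4, 6 and 8 (2, 3 and 4 parameters), so the sigmoid must lower the weighted residual sum of squares by more than 4 to beat log-linear. Often it does not, and the simpler curve errs upward at low dose and downward at 8 mg/g.

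**5. Simulation.** Binomial counts at 0, 1, 3, 8, 20 mg/g; arm logits with inverse-variance weights; three models fitted by generalised least squares; AIC = weighted RSS + 2k; delta-method CI from the selected model; 4000 trials per scenario in the main runs (Monte Carlo error under 1 point).

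Reading A, coverage at the worse of 1 and 3 mg/g: flat 95%; log-linear or Emax 84-92%; sigmoid 79-90% (h 1.5), 72-86% (h 2), 61-82% (h 3).

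By dose, h 2 to 3:

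| True ED50 | 1 mg/g | 3 mg/g | 8 mg/g |
|---|---|---|---|
| 2 | 66-87% | 75-89% | 87-88% |
| 3 | 68-85% | 92-94% | 76-88% |
| 4 | 78-86% | 78-90% | 78-91% |
| 6 | 84-92% | 61-75% | 92-96% |

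Separately coded runs agree. For h 2 to 3 the worst of the three doses had 53-86%, and AIC chose the true sigmoid in 14-38% of trials. For h 4 and ED50 1 to 15 the worst dose had 65-84% (c 0.2) or 60-75% (c 1). If the whole rise lies below 1 mg/g (ED50 0.3-0.5), the loss is small: 87-89% (c 0.2) or 93-94% (c 1).

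**6. Cause.** Always fitting the sigmoid gave 94-98% at 1, 3 and 8 mg/g. The logit approximation and delta method are therefore not to blame.

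**7. Direction, h 2 to 3.** The whole band lies above the truth at 1 mg/g (ED50 2 to 4) or 3 mg/g (ED50 6) in 12-39% of trials, against 2.5% nominal; the true response there is 15-20%. At 8 mg/g (ED50 2 to 4) nearly all misses are bands below the truth. At 3 mg/g with ED50 2 (true response 34-37%) bands also fall below, in 10-25% of trials.

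**8. Other settings, worse low dose.**

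| Setting | Sigmoid, h 2-3 | Log-linear or Emax |
|---|---|---|
| Top response 35% | 64-88% | 86-93% |
| 37 per arm (baseline IGA 3-4) | 62-87% | 86-93% |
| Adjusted for region and IGA | 65-87% | 83-92% |
| HECSI, effect 0.5-1.0 SD (assumed) | 63-90% | 79-93% |

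The 37 follows from section 7.2: 50 to 75 mild subjects leave 175 to 200, or 35 to 40 per arm. Among trials passing the contrast test (94-99%), coverage is 61-88% for h 2 to 3.

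**9. Reading B, worst of 1, 3 and 8 mg/g.** Right guesses: 80-94% (sigmoid), 88-94% (Emax), 90-93% (log-linear). Wrong guesses: 22-93%, where misfit adds to selection.

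**10. Bootstrap repeating selection and fit, Reading A.** Coverage at 1, 3 and 8 mg/g: 87-99% (50 per arm), 90-98% (37 per arm), 91-99% (adjusted), 92-99% (HECSI, 0.75 SD). Of 9 truths × 2 values of c × 3 doses × 4 settings = 216 values, one is below 90%. Separate runs at other settings raised the worst dose from 52-73% to 81-93%. Under Reading B it gives 90-97% with right guesses, but with wrong fixed guesses it does not help (24-87% at 3 mg/g).

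**The case against.** The strongest reply is about consequence. When the band misses upward, its lower edge clears the truth by a median of only 1.2-2.5 percentage points, and the mean bias of the curve at those doses is 2.0-3.9 points (2-5 in another set of runs), against bands 13-20 points wide. Readers will also see the observed rates and the CMH comparison for each dose, and for HECSI an MMRM estimate with CI. The plan has no numerical dose-selection rule, so no changed choice can be shown. All of this stands and limits the harm; none of it makes the stated 95% correct.

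Second, ED50, h and c are unknown, and nothing in the documents shows that h of 2 or more is likely. That is so, and the size of the loss depends on them. But the sigmoid is one of the plan's own candidates, and some loss appears for log-linear and Emax truths too.

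Third, Reading B is arguably the more literal, and the CI method is not named. Fixing the shape does not escape the problem unless the guesses are right. Although the delta method is an assumption, basing the CI on the selected model points to an interval conditional on that model.

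Fourth, the bootstrap restores coverage only in part. That also stands.

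**Conclusion.** The concern holds. As written, the 95% CI is conditional on the AIC-selected model and makes no allowance for the selection. With 50 per arm, response rising from 15% to 45%, and ED50 and h estimated, coverage at the worse of 1 and 3 mg/g is 61-86% for sigmoid truths with h 2 to 3, 79-90% with h 1.5, and 84-92% for log-linear or Emax truths. The ranges rest on assumed ED50, h and c and on a delta-method CI. The typical error is a few percentage points, upward at the low end of a steep curve and downward on or above its rise. The pairwise CMH tests and the sample size are unaffected. The CI should be corrected before the SAP is finalised; confidence in the exact size is medium.

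**What to change.** Keep the contrast test and AIC. In the SAP:

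- State that ED50 and h are estimated in the modelling step, with the guesses used only for the contrasts.
- Form the presented 95% CI for the IGA TS curve by a bootstrap that repeats model selection and fit in each resample.
- Use the same method for the baseline IGA 3-4 subset and for HECSI.

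The cost is SAP wording and a little extra R code; sample size and conduct do not change. Bands widen at 3 mg/g from 13-18 to 16-22 percentage points (mean increase 4), and by about 2 points at 1 and 8 mg/g. Coverage improves but is not guaranteed: the worst value was 87% in the main runs and about 81% at other settings.

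Always fitting the sigmoid is an alternative with better coverage (94-98%), but its band at 3 mg/g is 5-9 points wider than the planned one, against 2-5 for the bootstrap.
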